#### Ethics Committee

**ECs** The registry will be submitted to the EC of the PI, to the Ethics Commission of the Universität Leipzig as a leading EC and/ or the relevant ECs of the participating sites.

## Sponsor

Topera Inc., Palo Alto as sponsor for the Registry

## Synopsis

### Introduction

Atrial fibrillation (AF) is the most common sustained arrhythmia in man, and has an increasing population prevalence over time. Treatment is aimed at stroke prevention on the one hand, and amelioration of symptoms (palpitations, lightheadedness, dyspnea, fatigue) due to the arrhythmia. Medical therapy often fails to render a satisfactory response for the latter, prompting the search for alternative therapies. Surgical and, in the last 15 years, catheter ablation techniques have been devised to try to prevent episodes from starting. Groundbreaking work by Haïssaguerre showed that premature discharges or rapid repeated firing from the pulmonary veins (PVs) could trigger AF episodes and that electrical isolation of the PVs could potentially cure the patient of AF. PV isolation currently is a painstaking process consisting of delivering radiofrequency energy in the left atrium to isolate these veins. Such procedures take 3-5 hr to complete depending on the complexity of the individual case, and a large percentage of patients require a 2nd or even 3rd procedure to achieve acceptable antiarrhythmic results. Despite considerable investigative effort, the exact pathophysiology of how PV triggers initiate and/or maintain episodes of AF has been elusive.

Recently, Narayan et al have developed an algorithm that has been licensed for use with a novel mapping technology (RhythmView, Topera, Inc, Palo Alto, CA) for analyzing atrial recordings during human AF, finding that >95% of cases demonstrate either a rapidly spinning rotor (small circuit) or very rapid focal impulse formation. Furthermore, they have shown that catheter ablation at these relatively circumscribed areas can significantly affect AF, either by substantial slowing of the rate or termination (to an atrial tachycardia or sinus rhythm). In the CONFIRM (CONventional vs Focal Impulse and Rotor Modulation) trial, patients were treated with either conventional mapping and ablation (largely PV isolation or PVI) vs ablation of rotors or sites of focal impulse formation as designated by the mapping algorithm, followed by conventional ablation (PVI). The authors found much higher acute and long-term efficacy when focal impulse and rotor modulation (FIRM ablation) was used (82.4 vs 44% freedom from AF at 24 months post procedure). Although CONFIRM was a controlled registry, a randomized evaluation would be warranted.

E-FIRM is a registry to track Topera Inc.'s FIRM products in terms of clinical usage, handling, and the safety and effectiveness of FIRM procedures for the treatment of symptomatic atrial fibrillation. There will be at least 150 patients enrolled in this registry

### Safety endpoint

Safety shall be evaluated both acute and long term.

| Endpoint          | Description  |
|-------------------|--|
| Acute success     | Freedom from major adverse events related to the procedure within seven days of the procedure.   |
| Long-term success | Freedom from cumulative major adverse events related to the procedure (including any repeat procedures required) within one year of the initial procedure. |

---

**Primary Efficacy endpoint** Efficacy endpoints are defined in the table below.

| Endpoint                       | Definition  |
|--------------------------------|---|
| Acute success of FIRM ablation | The acute success of FIRM guided ablation is defined as elimination of the rotors defined by absence of rotors in the FIRMap.   |
| Long term success              | Two sequential endpoints will be used for long term efficacy after the initial AF ablation procedure (only):
(1) Single Procedure Freedom from AF recurrence* at 3 months, and
(2) Single Procedure Freedom from AF recurrence* from 3-12 months after the initial AF ablation procedure

*Freedom from AF recurrence is defined as: No document episodes of AF >30 sec with conventional noninvasive monitoring or, in the case of an cardiac implanted electronic device (CIED), <1% AF noted overall and no episodes of AF>30 sec. |

The design of the registry is summarized in the table below.

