## Adverse Events

**Overview** All adverse events (unanticipated and anticipated) must be classified as serious or minor.

**Definitions** The table below describes the classifications of adverse events (AE). All major adverse events occurring during the registry will be included in the safety analysis.

| Term        | Definition   |
|-------------|--|
| Serious     | 
Any adverse event which occurs following use of the device and:
 
 
• is life-threatening*;
 
• results in permanent impairment of a body function or permanent damage to a body structure; or
 
• necessitates significant intervention, such as major surgery, to prevent permanent impairment of a body function or permanent damage to a body structure; or
 
• requires hospitalization or an extended hospital stay; or
 
• results in moderate transient impairment of a body function or transient damage to a body structure; or
 
• requires intervention such as medication or cardioversion* to prevent permanent impairment of a body function or damage to a body structure**.
 
 |
| Minor       | 
Any adverse event that occurs following use of the procedure that results in minimal transient impairment of a body function or damage to a body structure, or which does not require any intervention other than monitoring.
   |
| Anticipated | 
Anticipated or known possible adverse events associated with cardiac electrophysiology procedures (see detail listing below in “Anticipated AE”)
  |

| Term          | Definition                                       |
|---------------|--|
| Unanticipated | EU guideline and requirements will be applicable |

\* In this context, the term refers to an event in which the subject was at immediate risk of death at the time of the event; it does NOT refer to an event that might have caused death if it were more severe.

\*\* For example, if the occurrence of a “catheter insertion site hematoma” or an “AV fistula” requires a blood transfusion and/or surgical repair, it should be considered a major adverse event.

**Anticipated AE** Anticipated adverse events include:

| Description   | Description   |
|---|---|
| Discomfort due to insertion/removal of vascular sheaths beyond what is normally observed  | Ventricular arrhythmia requiring defibrillation                                 |

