| Hemorrhage and/or hematoma at sheath insertion requiring evacuation or transfusion  | Cardiac tamponade due to perforation  |
| Extremity weakness, swelling, and/or pain   |   |
| Discomfort and/or damage to the skin, muscles, or nerves due to remaining in a supine position for an extended period of time.                  | Nerve injury (diaphragmatic paralysis, pyloric spasm, gastric hypomotility)     |
| Complete AV block   | Air embolism  |
| Nausea /vomiting  | Allergic reaction   |
| Headache different from baseline  | Endocarditis  |
| Hypertension >180 mm Hg systolic (repeated measures)  | Esophageal-atria fistula  |
| Hypotension <80 mm Hg systolic (repeated measures)  | Hemothorax  |
| Brief “black out” periods   | Pericarditis  |
| Shortness of breath/Dyspnea   | Pseudo aneurysm   |
| Feeling of chest pain, skipped beats, and/or rapid heart rate different from baseline   | Pulmonary vein stenosis   |
| Damage to skin from prolonged exposure to x-rays  | Radiation injury  |
| New arrhythmias (not previously documented)   | Renal failure form IV contrast  |
| Arterial injury requiring intervention  | Respiratory failure   |
| Thromboembolism   | Stroke/TIA  |
| Local/systemic infection  | Valvular damage   |
| Pneumothorax  | Pleural effusion  |
| AV fistula  | Pulmonary edema   |
| Thrombophlebitis  | Anemia requiring transfusion  |
| Pulmonary embolism  | Vasovagal reaction  |
| Myocardial infarction   | New pericardial effusion >1 cm  |
| Discomfort and/or damage to the skin, muscles, or nerves due to percutaneous access in excess of usual  | Death (must be reported within the regulation of serious adverse events) |
| Left heart access via trans-septal puncture has known potential adverse events of: cardiac perforation, cardiac tamponade, and embolic events.* |   |

\* Literature reviews have demonstrated that the risk of such events are <1%.  
 Mullins, Charles E. "Trans-septal left heart catheterization: Experience with a new technique in 520 pediatric and adult subjects." Pediatric Cardiology, v. 4, pgs. 239-246 (1983)

**Occurrence** The table below describes actions taken for adverse events that occur during and after the procedure.

| Timing          | Action  |
|-----------------|---|

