| Intra-procedure | If the investigator determines that an adverse event occurs while the patient is in the electrophysiology lab (before or during the procedure), the investigator shall manage the patient as he/she would if a similar event occurred during a standard EP procedure. |
| Post-procedure  | Once the patient has left the electrophysiology lab, all medical/surgical management will be carried out in the standard manner for that institution  |

**Reporting SAEs, & deaths** Reporting requirements for deaths or other adverse events considered to be serious or unanticipated are described in the table below.

| Report to                    | Reporting Requirements  |
|------------------------------|---|
| Principal Investigative Site | Must be reported according to the rules of the respective Ethics Committee  |
| EC                           | 
Report of the adverse event to the site's Institutional Review Board is the responsibility of the Principal Investigator.
 
The investigator is responsible for reporting such events to their EC within 10 working days of knowledge of the event.
 
Adverse events clearly unrelated to the device (e.g., broken limb, malignancy) may be reported in accordance with institutional requirements and recorded on CRFs as appropriate
 |

Details are found in Medical Event Report Form "MERF" below.

**MERF** The table below describes the information required on the initial and final MERF reports.

| Information   | Initial | Final |
|---|---------|-------|
| Patient registry number   | ✓       | ✓     |
| Gender  | ✓       | ✓     |
| Date of birth   | ✓       | ✓     |
| Date of procedure   | ✓       | ✓     |
| Adverse experience/complication and classification (major/minor)                  | ✓       | ✓     |
| Period of hospitalization (if required)   | ✓       | ✓     |
| Investigator's opinion as to the relationship of event/complication to the device | ✓       | ✓     |
| The disposition of the device (if returned, provide date)                         | ✓       | ✓     |
| Description of the event or problem   | ✓       | ✓     |
| Classification of event (anticipated/unanticipated and minor/major)               |         | ✓     |
| Date of onset   |         | ✓     |
| Date of resolution  |         | ✓     |
| Date of discovery   |         | ✓     |
| Reporter name, title, and contact information                                     |         | ✓     |
| Patient outcome   |         | ✓     |

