| Treatment or therapy used to treat  |         | ✓     |
| Relevant laboratory tests   |         | ✓     |
| Relevant history, including pre-existing medical conditions                       |         | ✓     |
| Suspect device name, part number, and lot number                                  |         | ✓     |

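### Both safety endpoints count procedure-related major events, but the only causality item listed for event reporting is relationship to the device, and the Adverse Events section takes in major events of any cause

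*Protocol*

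**What the plan says.** The Safety endpoint table in the Protocol synopsis gives two endpoints. The acute one is "Freedom from major adverse events related to the procedure within seven days of the procedure". The long-term one is "Freedom from cumulative major adverse events related to the procedure (including any repeat procedures required) within one year of the initial procedure". Both rest on attribution to the procedure; only the second extends to repeat procedures.

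The Adverse Events section lists what the initial and final MERF must contain. The one item asking for a causal judgement is "Investigator's opinion as to the relationship of event/complication to the device". Other items nearby are "Classification of event (anticipated/unanticipated and minor/major" and "Suspect device name, part number, and lot number", neither of which asks whether the procedure caused the event. The form also carries a procedure date, an onset date and a description.

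The Definitions paragraph of the same section places every major event during the registry in the safety analysis, with no condition on cause. The ethics committee row of the reporting table allows a lighter reporting route for events plainly unconnected with the device; it does not mention the procedure.

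**The concern.** An endpoint defined by attribution needs that attribution recorded, preferably by the investigator when the event is reported. Here the endpoint asks about one exposure (the procedure) and the listed form asks about another (the device). A third statement, in the Definitions paragraph, asks about neither.

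Whoever computes the complication rate from the listed items has to choose a substitute or attribute events afterwards. Safety is one of the stated purposes of the registry, so the reported rate is a main result, and its value could depend on a choice that the protocol leaves open. An analysis plan can choose between sets of events, but it cannot supply an investigator's judgement that was not collected.

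**Working it through.** No figure in the protocol can be reproduced here; the check is a comparison of the text.

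**Step 1. Which events each place selects.**

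| Place in Protocol | Events selected | Attribution needed |
|---|---|---|
| Synopsis, Safety endpoint, acute | major, within seven days | procedure |
| Synopsis, Safety endpoint, long-term | major, cumulative to one year, repeats included | procedure |
| Adverse Events, Definitions | all major | none |
| Adverse Events, MERF | each reported event | device |

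**Step 2. Count of form items.** The MERF table has 19 items. One is a causality item (device). None records relationship to the procedure.

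**Step 3. Is device the same as procedure?** No. The Sample Size row of the synopsis defines FIRM-guided ablation without regard to any further ablation, and the ablation procedure description allows conventional ablation, mostly pulmonary vein isolation, alongside it. The anticipated-event list states that "Left heart access via trans-septal puncture has known potential adverse events of: cardiac perforation, cardiac tamponade, and embolic events". An investigator could properly mark a tamponade from trans-septal puncture as not device-related, although it is an endpoint event.

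**Step 4. Can the anticipated/unanticipated item stand in?** No. Anticipated events are defined as "Anticipated or known possible adverse events associated with cardiac electrophysiology procedures", which describes a type of event and not the cause of a particular one. The list includes stroke/TIA and "Myocardial infarction". Either of these, occurring months later, may or may not be due to the ablation.

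**Step 5. Direction of error.** Let D, P and A be the patients with at least one major event in the window that is device-related, procedure-related or of any cause. Assume that a device-related event is also procedure-related, since the device is used within the procedure. Then D is contained in P and P in A, so

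rate(D) ≤ rate(P) ≤ rate(A).

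The endpoint is rate(P). The device item gives rate(D), which is too low or equal. The Definitions paragraph gives rate(A), which is too high or equal.

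**Step 6. Size per patient.** The synopsis gives a minimum enrolment of n = 150. A patient whose only qualifying event is wrongly left out or put in changes the rate by 1/n = 1/150 = 0.00667, or 0.67 percentage points. With more patients the step is smaller. The protocol gives no event rate and no split by relatedness, so the number of such patients cannot be estimated.

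**The case against.** The strongest reply is that the MERF is an event-reporting form and not the endpoint dataset. It appears under the reporting of serious events and deaths. The Data Collection section sends registry data to an online database, and the reporting table mentions case report forms separately. The fields of neither are shown, and nothing says that the endpoints are computed from the MERF. This stands as a limit: a reader might infer that procedure relatedness is not collected at all, and the protocol does not show that. It shows only that the listed items do not contain it.

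Later attribution is also often possible. Adverse event review is scheduled during the procedure, at day 7-10 and at 1, 3, 6 and 12 months. AF interventional procedures are recorded from 1 month on, and the MERF has dates and a description. For the seven-day endpoint, close timing leaves little doubt. For late events timing does not settle cause, and the one-year endpoint includes these. The protocol describes no adjudication.

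Four stronger readings are tempting but not supported:

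- *The form needs an item separating index from repeat procedures.* The one-year endpoint pools them, and procedure and onset dates give the seven-day window.
- *The Serious definition filters by device causality.* Its reference to use of the device concerns timing, not cause.
- *The exception for events unconnected with the device removes endpoint events.* It stands in the ethics committee reporting row, its examples are not procedural complications, and it still provides for recording on case report forms as appropriate.
- *Serious and major are two different classes.* The footnote to the Serious definition uses them interchangeably; the wording is untidy, nothing more.

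Finally, one may say that the Definitions paragraph protects against loss, because it keeps all major events. It does so for the safety analysis in general, but it describes a different set from the endpoints and does not supply the missing attribution. It is part of the inconsistency as well as a safeguard.

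**Conclusion.** The point holds for the listed items and should be fixed. The protocol states a procedure-related endpoint, lists a device-related causality item, and elsewhere describes an any-cause safety analysis; these are three different sets of events. Followed as listed, the form does not collect the judgement on which both endpoints depend.

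A reader might infer that events will be lost or that the reported rate will be too low. Neither is certain: nothing in the protocol filters events by device relatedness, and the error could go either way depending on the substitute used. The conclusion rests on two assumptions: that no procedure-relatedness field exists in the database or case report forms that are not shown, and, for the direction of error, that device-related events are also procedure-related. The protocol states no safety margin or test, so the reported rate is affected and no pass/fail decision is.

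**What to change.** 1. Add an investigator item, *relationship to the procedure (initial or any repeat)*, to the MERF and the database, beside the device item. If the database already holds it, say so in the protocol; that closes the main gap.
2. State under Safety endpoint that both endpoints use this item.
3. Reconcile the Definitions paragraph with the Safety endpoint table, for example by reporting all major events, whatever their cause, as a separate supportive summary.
4. As secondary wording changes, extend the ethics committee reporting exception to events clearly unconnected with both device and procedure, and use one term for major and serious throughout.

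The cost is one form item and a few sentences. If data collection has begun, the item must be completed retrospectively for events already reported. The reported complication rate may come out higher than one based on the device item.

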**Registry design**

| Item   | Description  |
|--------|--|
| Design | This is a prospective registry to assess the safety and effectiveness of FIRM procedures for the treatment of symptomatic any type of atrial fibrillation. |

|                     |  |
|---------------------|--|
| Sample Size         | Each site will enroll all FIRM-guided patients undergoing AF ablation into this registry up to at least overall 150 subjects. FIRM-guided ablation is defined as ablating FIRM identified rotors independent of any additional ablation. |
| Randomization       | The registry is non-randomized but consecutive.  |
| Investigators       | Up to 2 investigators per site   |
| Investigative sites | Up to 10 investigative sites within Germany / Europe   |

|                           |   |
|---------------------------|---|
| Patient population | Subjects eligible for participation in the registry should be in accordance to the AF guidelines:

 
Reported incidence of at least two (2) documented episodes of symptomatic AF (paroxysmal, persistent or long standing persistent) during the three months preceding trial entry (at least one episode should be documented by rhythm strip or ECG).
 
Attempt of at least one Class I or III anti-arrhythmia drug with failure defined as recurrence of symptomatic AF or adverse drug effect resulting in stopping the medication.
 
 |
|---------------------------|---|

|                          |   |
|--------------------------|---|
| Registry schedule | The registry visits schedule will follow the standard routine procedure of each site. Proposed activities during the visits are described in the table below. Since this is a registry, these are data items that will be collected, if available, as consistent and applicable with routine and standard clinical care at each site. |
|--------------------------|---|

| Visit Timing                           | Description   |
|--|---|
| Procedure and immediate post-procedure | Cardiac ablation procedure (see "Ablation Procedure" for details). During the procedure, the patient will be monitored for adverse events. Appropriate clinical measures will be taken to treat the adverse event, should one occur.  |

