| Seven-Ten Days Post Procedure          | The following assessments/procedures will be performed: 
 
Symptom and rhythm assessment per defined follow up monitoring
 
Follow up to assess for adverse events
 
  |
| Three Months Post Procedure            | The following assessments/procedures will be performed: 
 
Diagnostic 12-lead ECG
 
48-hr or 72-hr ambulatory continuous ECG monitor (Holter) or CIED interrogation, if applicable
 
Symptom and rhythm assessment per defined follow up monitoring
 
Concomitant anti-arrhythmic medications
 
Adverse events
 
 |
| Six Months Post Procedure              | The following assessments/procedures will be performed: 
 
Diagnostic 12-lead ECG
 
48-hr or 72-hr ambulatory continuous ECG monitor (Holter) or CIED interrogation, if applicable
 
Symptom and rhythm assessment per defined follow up monitoring
 
Concomitant anti-arrhythmic medications
 
Adverse events
 
 |

|                              |  |
|------------------------------|--|
| Twelve Months Post Procedure | 
The following assessments/procedures will be performed:
 
 
• Diagnostic 12-lead ECG
 
• 48-hr or 72-hr ambulatory continuous ECG monitor (Holter) or CIED interrogation, if applicable
 
• Symptom and rhythm assessment per defined follow up monitoring
 
• Concomitant anti-arrhythmic medications
 
• Adverse events
 
 |
|------------------------------|--|

|   |  |
|---|--|
| Ablation procedure description   | Investigators should follow the standard procedure as defined by training from Topera Inc. and appropriate medical judgment for FIRM guided ablation with or without the conventional ablation procedure (mostly PVI) practiced at the individual site.  |
| Post procedure rhythm monitoring | According to routine and standard procedure of the site preferred would be for all subjects without CIED (having AF diagnostic algorithms) to receive a 48 or 72 hour Holter monitor at 3, 6, and 12 months post-procedure.  |
|   | AF symptoms should be documented as recurrent within the follow-up period, further treatment shall be at the discretion of the physician (e.g., drugs, re-ablation, etc.).   |

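### Without a CIED, long-term success means no documented AF >30 sec but is not conditional on a recording having been made, and the protocol words the monitoring inconsistently

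*Protocol*

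**What the plan says.** The long-term endpoint is in the Protocol Synopsis, in the table under Primary Efficacy endpoint. It has two parts: freedom from AF recurrence at 3 months, and from 3 to 12 months, each after a single procedure. For patients without a CIED, freedom from recurrence is "No document episodes of AF >30 sec with conventional noninvasive monitoring". For patients with a CIED, the rule adds an AF burden below 1%, which presupposes a device readout. The table sets no minimum number, type or duration of recordings and does not say how to classify a patient who has none.

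The monitoring that would produce the documentation is described in four places:

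- **Registry schedule.** "The registry visits schedule will follow the standard routine procedure of each site". The activities are introduced with "Proposed activities during the visits are described in the table below", and the protocol adds that "these are data items that will be collected, if available, as consistent and applicable with routine and standard clinical care".
- **Visit table.** At 3, 6 and 12 months the wording is firmer: "The following assessments/procedures will be performed". The list includes a 12-lead ECG and "48-hr or 72-hr ambulatory continuous ECG monitor (Holter) or CIED interrogation, if applicable".
- **Post procedure rhythm monitoring.** The Holter is a preference: "According to routine and standard procedure of the site preferred would be for all subjects without CIED" to receive it at 3, 6 and 12 months.
- **Registry data collection detail.** The grid marks the ambulatory monitor as a data field at 3, 6 and 12 months, and as applicable only in some cases at 1 month. The visit table and the grid both refer to a defined scheme of follow-up monitoring, but the protocol sets out no such scheme beyond the stated preference.

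**The concern.** The endpoint counts documented episodes, while parts of the protocol leave the documentation to site routine. A patient with no ambulatory recording and no other evidence of AF satisfies the literal rule, so absence of evidence can be scored as success. Such a patient is not missing under that rule. A missing-data provision in the SAP might therefore never apply.

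The registry has one arm, so no control group would show the same effect. Up to 10 sites each follow their own routine, so completeness of monitoring may also differ by site, and differences in success between sites could partly be differences in recording.

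**Working it through.** The protocol gives no figure for this point, so there is nothing to reproduce. The check is of direction first, then an illustration of size.

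**Direction.** Take as reference the success rate the same patients would show under the preferred 48 or 72 hour Holters. If a patient receives less monitoring than that, a recurrence can go undocumented, but no recurrence can be added. For these patients the shift is zero or upward. If a site's routine is more intensive than the preferred Holter, it may document more AF than the reference, and the argument does not apply to its patients.

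**Inputs (all assumed, none in the protocol).**

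- p = success rate as classified under the preferred monitoring; 60% for illustration.
- m = share of all patients without an adequate recording in the window; 10% and 30%.
- s = share of those patients' recurrences documented in some other way, such as a visit ECG or a symptom-driven recording; 50% and 100%, with 0% as an extreme.
- Recurrence is taken to be equally frequent with and without a recording.

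**Formulas.**

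- As-written rate = p + m(1-p)(1-s), so bias = m(1-p)(1-s).
- Rate with unknown counted as failure = (1-m)p.
- Share with unknown status = m[1 - s(1-p)].

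**Results at p = 60%, with counts for the minimum enrolment of 150.**

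| m | s | Bias (points) | As-written | Unknown = failure | Unknown, of 150 |
|---|---|---|---|---|---|
| 10% | 0% | 0.1 x 0.4 x 1 = +4 | 64% | 54% | 15 |
| 10% | 50% | 0.1 x 0.4 x 0.5 = +2 | 62% | 54% | 12 |
| 10% | 100% | 0 | 60% | 54% | 9 |
| 30% | 0% | 0.3 x 0.4 x 1 = +12 | 72% | 42% | 45 |
| 30% | 50% | 0.3 x 0.4 x 0.5 = +6 | 66% | 42% | 36 |
| 30% | 100% | 0 | 60% | 42% | 27 |

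**Sensitivity to p.** The Introduction cites freedom from AF of 82.4% and 44% at 24 months in an earlier controlled registry. At m = 20% and s = 50% the bias is 0.2 x 0.176 x 0.5 = 1.8 points at the first value and 0.2 x 0.56 x 0.5 = 5.6 points at the second.

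**Scale.** The 95% half-width at p = 60% and n = 150 is 1.96 x sqrt(0.6 x 0.4/150) = 7.8 points. Bias does not shrink with more patients, but at s = 50% it stays below this half-width in the table.

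**Evaluable-only rate.** If unknown patients are dropped while documented recurrences stay in, the rate is (1-m)p / [(1-m) + m(1-p)s]. At m = 30% this is 0.42/0.76 = 55.3% for s = 50% and 0.42/0.82 = 51.2% for s = 100%, which is 4.7 and 8.8 points below p. Dropping the unknowns therefore introduces a bias in the other direction.

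**Limit of the reference.** The 3-month Holter covers 2-3 of about 91.3 days (2.2-3.3%). The 6- and 12-month Holters cover 4-6 of about 273.9 days (1.5-2.2%). So p is success as detected under that schedule, not true freedom from AF.

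**The case against.** The strongest reply is that the definition mentions conventional noninvasive monitoring, and its ordinary reading is that monitoring was done and showed no AF. The protocol nowhere says that an unrecorded patient is a success. This is fair as far as it goes: the phrase suggests monitoring. It does not require it, and two readers could classify the same patient differently.

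A reader might infer that monitoring is simply optional. The documents do not support that. ECG and Holter are scheduled at 3, 6 and 12 months in the visit table and have data fields in the grid, and the words on applicability in the visit table may attach to device interrogation alone. The defect is conflicting wording plus a success rule that depends on none of it.

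A reader might also infer that the registry's rate must be too high. That does not follow either. The upward direction holds only for patients monitored less than the preferred schedule, and some sites may monitor more.

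Reliance on routine care is a declared choice for a registry, and handling of missing data and choice of estimator belong in the SAP. Both points stand. The definition of success, however, is fixed in the protocol, and a patient who meets it literally never becomes a missing-data case.

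Finally, the protocol states no performance goal or comparison that this rate must meet. That limits the consequence but does not settle the ambiguity.

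**Conclusion.** The point holds in this form: for patients without a CIED, success is not conditional on a recording, the monitoring wording conflicts, and a patient with no ambulatory recording in the window can be counted as free of AF. Relative to the preferred schedule, the bias is zero or upward among patients monitored less than that schedule.

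The size is unknown. With p = 60%, m = 10-30% and s = 50%, it is about +2 to +6 points; it is 0 if all recurrences in unrecorded patients are documented otherwise. The +12 points at m = 30% needs every such recurrence to go undocumented. That is an extreme, because visit ECGs and symptom assessments would find some, so a shift of that size should not be presented as expected.

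This should be fixed, with medium confidence: the gap is plain in the text, its effect is not measurable from it, and the correction is inexpensive.

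**What to change.** 1. **Endpoint definition (Primary Efficacy endpoint table).** State that any documented AF >30 sec in the window is a recurrence. A patient without one counts as a success only if an adequate recording exists in that window: an ambulatory ECG of at least 48 hours (longer recordings qualify), or interrogation of a CIED with AF diagnostic algorithms. Apply this at the 3-month visit for the first endpoint and at the 12-month visit for the second. A patient with only a 6-month recording has a known status only up to that date.
2. **Unknown status.** Classify other patients without documented recurrence as rhythm status unknown, not as successes.
3. **Reporting.** Give the share with adequate monitoring at 3, 6 and 12 months, overall and by site. Show the success rate with unknown counted as failure beside the as-written rate. Leave the estimator to the SAP, but do not use the evaluable-only rate alone.
4. **Wording.** Reconcile the Registry schedule, the visit table, Post procedure rhythm monitoring and the data collection grid, so that the status of the recordings is the same throughout and the follow-up monitoring described as defined is actually set out.

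**Cost.** Definition and reporting text only; no extra visits or tests. Fewer patients will have a known status, and the reported result will be wider or less favourable. At p = 60% and s = 50%, the two rates would be 54% and 62% at m = 10% (12 of 150 unknown), and 42% and 66% at m = 30% (36 of 150 unknown).
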